**Figure 3: IL-15 Levels**

An important cause of the PK and stimulation differences to be eliminated was the development of rhesus macaque (rm) antibodies against human IL-15. The rhesus monkeys were evaluated for the presence of rm anti-IL-15 antibodies, and in the monkeys receiving CIV IL-15, 3 of 6 animals developed detectable levels of antibodies at some point during the test period. One animal became positive after the first course with a boost in the IL-15 titer in this animal positive after the second course. Another CIV animal became low titer positive after the second course and remained positive in the pre-course 3 assessment, and a third animal was observed to have antibodies to IL-15 that were just above the lower limit of detection of the assay in the pre-course 3 assessment. All 3 animals continued to have elevated titers after completing the third course of CIV IL-15. While the test animal that demonstrated anti-IL-15 antibodies after the first course of treatment and had the highest anti-cytokine titers throughout the experiments had somewhat lower WBC and ALC values measured for the first treatment course, this particular macaque and none of the other antibody-positive animals showed substantial differences in their lymphocyte expansion or pattern of lymphocyte subpopulations compared to animals that tested negative for anti-IL-15 antibodies. The underlying causes of the difference in the immune response observed in courses 2 and 3 treatment has not been fully explained and is still being assessed with samples obtained during these experiments.

The macaques also had an inflammatory cytokine analysis performed. At the time points measured in this study, IL-8 was the only cytokine that gave values that were within the detection range of the standard curve, while all other samples had signals below the 2.4 pg/mL test standard. It is possible that evaluation of secondary cytokine induction would be more successful if the focus was on early time points such as 4, 8 and 24 hours after initiation of continuous infusion that have been measured in the ongoing IVB trial and are planned for this trial.

Compared to NHP that had received 20 mcg/kg/daily as an IVB for 12 days, the animals receiving 20 mcg/kg/daily CIV for 10 days had more constitutional and gastrointestinal side effects, as well as biochemical laboratory abnormalities that were most noticeable after the

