### **3 STUDY IMPLEMENTATION**

#### **3.1 STUDY DESIGN**

This is a Phase I open-label, non-randomized, dose-escalation safety trial of CIV rhIL-15 that will enroll 41 to 47 evaluable patients with metastatic unresectable cancers for which curative or palliative measures either do not exist or are not associated with a survival advantage.

Patients will receive CIV rhIL-15 for 10 consecutive days (240 hours) and will be assigned to a dose level sequentially based on their order of entry into the study. The starting dose will be 0.1 mcg/kg/day and in the absence of significant toxicities, dose escalation will proceed to evaluate dose levels of 0.25, 0.5, 1, 2 and 4 mcg/kg/day. Cycles 1 and 2 will be 42 days in length, but all subsequent treatment cycles will be 28 days in length with an additional 7 days on either schedule allowed for reasons other than recovery for treatment-related toxicities. Subjects will have to demonstrate an absence of anti-IL-15 antibodies in their post-treatment (day 12 and week 4) assessments before additional cycles of rhIL-15 can be initiated.

Radiologic reassessments for 10-day treatment cycle patients will be performed during week 4 (days 26 to 35) of Cycles 1 and 2 and at off-treatment and off-study visits.

After treatment of patients in the expansion cohort for the 10-day schedule is completed, new cohorts of 3 to 6 patients each will begin treatment with the 5-day (120 hour) schedule at dose levels of 3, 4 or 5 mcg/kg/day to define the MTD for this shorter CIV rhIL-15 regimen. All treatment cycles for these cohorts will be 21 days in length.

As of April 2016, twenty-four evaluable patients have enrolled on Dose Levels 1-6; with 2 more to be enrolled in Dose Level 6 after Amendment G. When the study is re-opened for enrollment, an additional 17-23 evaluable patients will be enrolled.

A total of 9 patients will potentially be treated at the MTD or maximum administered dose for both schedules to better characterize the clinical activity of CIV rhIL-15 in this patient population.

Radiologic reassessments for both the 10day and 5-day dosing cohorts will be performed after every other cycle (2, 4, 6, 8 etc.) including the subjects that go onto to receive additional cycles of treatment.

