#### **3.10.1 Off-Treatment Criteria**

- DLT as defined in Section [3.2](#).
- Persistent (> 14 days) treatment-related grade 2 (non-DLT) adverse events.
- Completion of protocol therapy
- Patient requests to be withdrawn from active therapy.
- Disease progression.
- No evidence of clinical response (i.e., patient has stable disease) on radiographic restaging after 2 consecutive cycles of treatment.
- The detection of anti-IL-15 neutralizing antibody serum titer  $\geq 500$  ng/mL as described in [APPENDIX C](#) prior to subsequent treatment cycles.
- Evidence the patient has developed auto-immunity that involves a vital organ (heart, kidney, brain, eye, thyroid or adrenal gland, colon, lung). Patients who develop new auto-antibodies without clinical evidence of end organ dysfunction will be seen by the appropriate Internal Medicine subspecialists to assess their risk for developing an autoimmune syndrome.
- Interruption of CIV rhIL-15 treatment for any reason for more than 24 consecutive hours during cycle 1. Stoppage of less than 15 minutes occurring during the daily change of the rhIL-15 infusion device will not be considered an interruption.
- Positive pregnancy test

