#### 5.1.4 Anti-IL-15 Antibodies

All samples will be drawn in 4 mL SST tubes; sampling will be performed for the days listed below **during all treatment cycles**. Labels listing the patient's name, date of birth, date and time of the blood draw will be affixed to all the tubes by the staff person who obtained the samples. For questions, please contact [name] Pharmacology Program (CPP) at [contact]; additionally, for pre-notification of planned samples (at least 24 hours in advance, the Friday

before is preferred) email [name] ([[contact]](mailto:[contact])) and [name] ([[contact]](mailto:[contact])). After sample collection, please page [name] for immediate pick-up. For any questions regarding sample processing, you may also contact [name] by e-mail or at [contact].

Samples will be held at room temperature until picked up by the [name] lab (Blood Processing Core) for processing and shipping of the samples to a Contractor for performance of the assays. Lymphoid Malignancies Branch Clinical Research personnel will arrange for these samples to be sent via courier to Clinical Support Laboratory in Frederick (specified above) for assay of the anti-IL-15 antibodies.

Sampling times for the 10-day infusion schedule are as follows:

- **Day 1 pre-treatment, days 12, 28 and off-treatment visit:** One SST tube will be drawn to assess for the formation of anti-IL-15 antibodies.
- Patients will have to demonstrate an absence of anti-IL-15 antibodies in their post-treatment (days 12 and 28) assessments before additional cycles of rhIL-15 can be initiated.

Sampling times for the 5-day infusion schedule are as follows:

- **Day 1 pre-treatment, days 6, 21, day 1 of subsequent cycles and off-treatment visit:** One SST tube will be drawn to assess for the formation of anti-IL-15 antibodies.
- Patients will have to demonstrate an absence of anti-IL-15 antibodies in their post-treatment assessments before additional cycles of rhIL-15 can be initiated.

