**3. Assay for antibodies to infused IL-15 (see [APPENDIX C](#)).**

## APPENDIX C: ASSAY FOR ANTIBODIES TO RHIL-15

- Plates are coated with human IL-15 for 3 hours at 37°C, washed, blocked with 3% FBS and washed again.
- A standard curve for assay quantitation and quality control is constructed using serial dilutions of a commercial affinity purified goat anti-human IL-15 that is diluted in heat-inactivated normal human serum. The standard curve samples are incubated for 2 hours at 37°C and washed.
- Biotin conjugated IL-15 is added to each well, incubated 2 hours at 37°C, and the plates are washed.
- Alkaline phosphatase-conjugated streptavidin is added to each well for 2 hours at 37°C and then washed.
- The assay is developed with the addition of diethanolamine buffer with p-Nitrophenyl Phosphatase for 1 hour at 37°C and then immediately read at 405 nm.
- To detect antibodies to human IL-15 in test samples, serum from the test subject will be assayed in duplicate at dilutions of 1/3 and 1/9 concomitantly with the standard curve samples as above, and the resultant OD obtained used to quantitate the level of antibody present.

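### Retreatment is barred by any anti-IL-15 antibody in Sections 3.1 and 5.1.4, but Section 3.10.1 stops treatment only at a neutralizing titer of at least 500 ng/mL and cites an assay with no neutralization step

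*Combined protocol and SAP*

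**What the plan says.** **Rule A, absence of antibody.** For the 10-day schedule, Section 3.1 states: "Subjects will have to demonstrate an absence of anti-IL-15 antibodies in their post-treatment (day 12 and week 4) assessments" before further cycles. Section 5.1.4 repeats this for that schedule ("Patients will have to demonstrate an absence of anti-IL-15 antibodies in their post-treatment (days 12 and 28) assessments before additional cycles") and sets the same condition for the 5-day schedule: "Patients will have to demonstrate an absence of anti-IL-15 antibodies in their post-treatment assessments before additional cycles of rhIL-15 can be initiated". None of the three statements gives a titer or mentions neutralization.

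**Rule B, neutralizing titer.** Section 3.10.1 lists among the off-treatment criteria "The detection of anti-IL-15 neutralizing antibody serum titer" of at least 500 ng/mL, refers to Appendix C for the assay, and applies the criterion "prior to subsequent treatment cycles". It is the only antibody criterion in that list.

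**Assay.** Appendix C coats plates with human IL-15, adds a labelled form ("Biotin conjugated IL-15 is added to each well"), and converts optical density to an amount of antibody using a goat anti-human IL-15 standard curve. Section 6.2.5.2 describes the immunogenicity method as a two-arm capture ELISA and points to Appendix B, whose antibody item points on to Appendix C. The Design part of the précis nevertheless describes the samples as testing for neutralizing antibody.

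**The concern.** One decision, whether a patient may start the next cycle, is governed by two rules that differ in threshold (none against 500 ng/mL) and in analyte (any antibody against neutralizing antibody). The assay cited for the second rule does not measure the analyte it names. Staff who consult different sections could handle the same result differently.

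The antibody rule applies from cycle 2 onward. Section 3.1 gives 5-day patients four cycles to show responsiveness, so the rule helps decide who receives that exposure. It therefore bears on response rate, time to progression and safety over repeated cycles. There is also an indirect link to the design: under the Schema footnote, one confirmed response in the 5-day cohorts triggers an expansion to nine patients, and a response cannot appear in a later cycle that is not given.

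**Working it through.** The plan states no figure to reproduce, and no sample-size or power arithmetic applies. The check sets the rules side by side.

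**Step 1. Same decision point?** Yes. Rule A applies before additional cycles and Rule B before subsequent cycles.

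**Step 2. Do the rules agree for every possible result?** Let L be the lowest concentration the assay can call positive. The documents do not state L.

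| Result | Rule A (3.1, 5.1.4) | Rule B (3.10.1) |
|---|---|---|
| Nothing detected | Next cycle allowed | Criterion not met |
| Detected, from L to below 500 ng/mL | Next cycle not allowed | Criterion not met |
| 500 ng/mL or more by Appendix C | Next cycle not allowed | Undetermined: Appendix C does not show neutralization |

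The middle row is empty if L is 500 ng/mL or higher and contains possible results if L is lower. The disagreement over threshold is therefore conditional on L. The disagreement over analyte is not: a patient with binding but non-neutralizing antibody at any level fails Rule A and, read literally, does not meet Rule B.

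**Step 3. Can Appendix C establish neutralization?** Its steps are capture on coated IL-15, bridging with biotinylated IL-15, enzyme detection, and reading against a standard curve. These quantify antibody that binds IL-15. No step tests whether IL-15 activity or receptor binding is inhibited. The appendix does not use the word neutralizing and gives no positivity cut-off, detection limit or 500 ng/mL threshold. The 500 ng/mL figure appears only in Section 3.10.1. Without a positivity cut-off, absence in Rule A is itself undefined.

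**Step 4. Does the distinction between binding and neutralizing have substance here?** The macaque data in Section 1.2.1.3 suggest so. Antibody-positive animals on continuous infusion did not differ substantially from negative ones in lymphocyte expansion, although the animal with the highest titers had somewhat lower white cell and lymphocyte counts in course 1. Detected antibody was not shown to be neutralizing.

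**Step 5. How often might this arise?** In those animals, "3 of 6 animals developed detectable levels of antibodies at some point during the test period", that is 3/6 = 50%. One of the three was positive at low titer and one was just above the detection limit. No value is given in ng/mL, so no animal can be placed above or below 500. The data show only that low-level positivity can occur.

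**The case against.** The strongest reply is that the two rules can be read together. A quantitative ELISA needs a cut-off before a sample can be called negative, and 500 ng/mL is the only one in the documents, so absence may simply mean below 500 ng/mL. Alternatively, Section 3.10.1 may govern permanent removal while Sections 3.1 and 5.1.4 impose a hold. Section 3.10.1 also lists reasons to stop and does not say that a patient who meets none of them may be retreated. These readings are plausible, and they are why the threshold conflict is stated conditionally. But the available text states neither reading and describes no hold or retest, and neither reading supplies the neutralization step.

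A reader might infer three stronger points that the documents do not support:

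- **That the positive macaques are the cases on which the rules disagree.** No ng/mL values are given, and the macaque assay is not said to be that of Appendix C. The animals received a human protein. Only one was positive after the first course, and the third course came about nine months after the second. The IV bolus macaque study found no antibodies.
- **That the immunogenicity endpoint will be mislabelled.** Section 6.2.5.2 defines it by capture ELISA without calling the antibody neutralizing. The wording problem lies in Section 3.10.1 and the précis.
- **That the plan omits the human antibody rate.** Part of the background section is not in the available text, so it can be said only that the available text gives no rate.

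Two limits on impact also stand. Section 8 declares the secondary evaluations exploratory, and the Section 3.1 sentence concerns the 10-day schedule, whose MTD is already identified. For the 5-day cohorts the conflict is between Sections 5.1.4 and 3.10.1.

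**Conclusion.** The point holds. The current text contains two antibody rules for the same retreatment decision, and one of them names an analyte that its cited assay cannot establish. The threshold conflict assumes that the assay detects antibody below 500 ng/mL, which the documents neither confirm nor exclude. The analyte mismatch does not need that assumption; it follows from the assay steps in Appendix C and from no other antibody assay being named in the available text.

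The number of patients affected cannot be estimated. The reach is limited to cycle 2 and later: the exploratory response and time-to-progression results, repeat-cycle safety and, indirectly, the 5-day expansion trigger. A reader might infer that the MTD is at risk. It is not, because Section 8 bases the MTD on DLT in cycle 1, before the antibody rule operates; the planned sample-size calculation is likewise unaffected. This should be corrected, but it does not undermine the primary objective.

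**What to change.** Reconcile Sections 3.1, 5.1.4 and 3.10.1 into a single antibody rule that names one analyte and one positivity or action threshold, tied to the Appendix C assay and expressed in units that the assay is stated to report. Replace neutralizing with binding in Section 3.10.1 and in the précis, unless a neutralization assay is named and described. If a hold and a permanent stop are meant to be different actions, say so. Which rule or threshold is right is a clinical decision for the sponsor and investigator and is not judged here.

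The cost is wording in three sections, the précis and Appendix C. No added samples or patients are needed unless a neutralization assay is introduced.

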#### **3.10.2 Off-Study Criteria**

- Voluntary withdrawal of consent by the patient to participate in the study
- Patient non-compliance with treatment and research plans
- Initiation of another anticancer treatment
- Any new medical or psychiatric condition that, in the opinion of the PI, precludes the safe continuation of the study
- Death

#### **3.10.3 Off Protocol Therapy and Off-Study Procedure**

Authorized staff must notify Central Registration Office (CRO) when a subject is taken off protocol therapy and when a subject is taken off-study. A Participant Status Updates Form from the web site (<http://home.ccr.cancer.gov/intra/eligibility/welcome.htm>) main page must be completed and sent via encrypted email to: NCI Central Registration Office at

[[contact]](mailto:[contact]).

## **4 CONCOMITANT MEDICATIONS/MEASURES**

Patients will be followed and managed as clinically appropriate with IV fluids, anti-emetics, anti-pyretics or other standard interventions based on the experience gathered from the ongoing rhIL-15 IVB trial and other biological response modifier therapies.

#### **5.1.1 Pharmacokinetic (PK) Studies**

All PK samples will be drawn in 4 mL SST tubes and PK testing will be performed **only during the first treatment cycle**. Labels listing the patient's name, date of birth, date and time of the blood draw will be affixed to all the tubes by the staff person who obtained the samples. Please page [name] ([name] lab) for pick-up. Because each treatment day is a 24 hour infusion, the “day 10 treatment” ends on day 11. Samples will be held at room temperature until picked up by the [name] lab (Blood Processing Core) for processing and shipping of the samples to a Contractor for performance of the assays. At time points where PK and inflammatory marker cytokine or anti-IL-15 antibody analyses coincide (day 1 pretreatment, hours 8, 4, 24 post initiation of infusion, day 8 and 12) one or two 4 mL SST tube will be drawn to decrease total amount of research blood drawn and the serum aliquoted into vials prior to shipment to the respective reference labs. Patient identifiers will be removed prior to shipment per Section **5.2.1**.

Sampling times for the 10-day infusion schedule are as follows (cycle 1 only):

- **Day 1:** Timed samples will be drawn just before beginning treatment (baseline), and at 10 minutes, 1, 2, 4 8 and 12 hours ( $\pm$  30 minutes) after starting the CIV rhIL-15 infusion.
- **Day 2:** A single timed sample will be drawn 24 hours ( $\pm$ 1 hour) after starting the CIV rhIL-15 infusion.
- **Day 3:** A single timed sample will be drawn 48 hours ( $\pm$ 2 hours) after starting the CIV rhIL-15 infusion
- **Days 7, through 10:** Timed samples will be drawn each morning with routine AM laboratory samples. The time the sample was obtained must be recorded.
- **Post-treatment day 11 at completion of infusion and day 12:** Timed samples will be drawn at the end of the 240-hour infusion, 10 and 30 minutes, 1, 2, 4 ( $\pm$  30 minutes) and 24 ( $\pm$  2 hours) hours (day 12) after termination of the CIV rhIL-15 infusion.

Sampling times for the 5-day infusion schedule are as follows (cycle 1 only):

- **Day 1:** Timed samples will be drawn just before beginning treatment (baseline), and at

10 minutes, 1, 2, 4 8 and 12 hours ( $\pm$  30 minutes) after starting the CIV rhIL-15 infusion.

- **Day 2:** A single timed sample will be drawn 24 hours ( $\pm$ 1 hour) after starting the CIV rhIL-15 infusion.
- **Day 3:** A single timed sample will be drawn 48 hours ( $\pm$ 2 hours) after starting the CIV rhIL-15 infusion
- **Days 4 and 5:** Timed samples will be drawn each morning with routine AM laboratory samples. The time the sample was obtained must be recorded.
- **Post-treatment day 6 at completion of infusion:** Timed samples will be drawn at the end of the 120 hour infusion at 10 and 30 minutes, 1, 2, 4 hours ( $\pm$  30 minutes).

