A similar but less severe set of post treatment toxicities were seen in the 1  $\mu\text{g}/\text{kg}$  subjects with chills rather than rigors, less significant increases in temperature, but no appreciable BP changes. There was a very low frequency or absence of these post infusional events in the 0.3  $\mu\text{g}/\text{kg}$  dosing cohort. Serial analyses of inflammatory cytokine levels (IL-1 $\beta$ , IL-6, IL-8, IL-10 and TNF $\alpha$ ) showed marked increases in serum levels of these inflammatory cytokines that coincided with these clinical toxicities and was most closely matched with the IL-6 levels. As predicted by the NHP toxicology studies performed to support this trial appreciable expansion and activation was seen for T-cells and NK cells, but the increase in lymphocytes was statistically significant only for the group that received the 3  $\mu\text{g}/\text{kg}$  dose that produced a 10-fold increase in NK cells, a more than 3-fold increase in T-cells mostly due to expansion of the terminally differentiated (memory and effector memory) CD8 $^{+}$  cells. The half-life ( $t_{1/2}$ ) was approximately 2 1/2 hours with Cmax 47,800, 15,900 and 1260 pg/mL respectively for the 3 dose levels tested. There were no clinical responses, with stable disease as a best response. However, 5 subjects manifested a decrease between 10 and 30% in their marker lesions, with 2 of these subjects having improvement or clearance of some lung lesions.

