## **8 STATISTICAL CONSIDERATIONS**

The primary objective of this trial is to determine the safety, toxicity profile, DLT and MTD of CIV rhIL-15 administered for 10 consecutive days (240 hours) or 5 consecutive days (120 hours) in subjects with metastatic unresectable cancers for which curative or palliative measures either do not exist or are not associated with a survival advantage.

The secondary objectives include determination of rhIL-15 PK, including time to reach serum steady state, decline if any at later time points, changes in serum concentration associated with the expected lymphocytosis and decline following discontinuation of the CIV infusion; characterization of the biological effects of rhIL-15 on the percentages and absolute numbers of circulating lymphocyte sets (NK and T-cells) and T-cell subsets (naïve, central or effector memory subsets based on expression of CD56, CD4, CD8, CD45RO, CD45RA, CD28, CD95, CCR7 and CD62L) by flow cytometry and the plasma levels of pro-inflammatory cytokines. The potential antitumor activity of rhIL-15 will be assessed by the clinical response rate and time to progression in this patient population; and assessment of the nature of T-cell infiltration and cytokine and check-point inhibitor gene expression by analysis of pre- and post-treatment biopsies obtained from selected patients with easily accessible tumor deposits. All evaluations of these secondary endpoints will be considered exploratory.

There are 9 planned dose levels for this trial that will enroll 3 to 6 patients each using a modified Fibonacci design to define the MTD for CIV rhIL-15.

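### On the 5-day schedule, post-infusion PK sampling ends at 4 hours and the end-of-infusion sample is not clearly stated, so the decline after stopping is imprecise when estimated from those samples alone (minor)

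*Combined protocol and SAP*

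**What the plan says.** Section 5.1.1 lists the post-infusion PK draws separately for the two schedules, in cycle 1 only.

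- **10-day schedule:** "Timed samples will be drawn at the end of the 240-hour infusion, 10 and 30 minutes, 1, 2, 4" hours, then 24 h on day 12. Appendix D, the cycle 1 worksheet for this schedule, has a separate end-of-treatment tube and a 24 h tube.
- **5-day schedule:** "Timed samples will be drawn at the end of the 120 hour infusion at 10 and 30 minutes, 1, 2, 4 hours". The list ends there. The calendar in Section 3.8.2 marks PK on days 1 to 6 only. The appendices hold no cycle 1 worksheet for this schedule, so this sentence is the only detailed instruction.

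Section 8 includes among the PK aims the "decline following discontinuation of the CIV infusion", with no exception for the 5-day schedule. It classes all secondary evaluations as exploratory. Section 1.2.1.4 reports that the half-life in the completed 30-minute-infusion trial "was approximately 2 1/2 hours with Cmax 47,800, 15,900 and 1260 pg/mL respectively". Section 5.1.1 also requires that the "date and time of the blood draw will be affixed to all the tubes".

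**The concern.** The two schedules share one PK aim but not one sampling plan, and no reason is given for the difference. The 5-day sentence can be read as starting at 10 minutes, which leaves the plateau value at the moment of stopping unsampled. It then stops while a sizeable part of the drug is still circulating. A slope fitted over so short a span is sensitive to assay noise, and a slower late phase would not be seen. PK is not repeated in later cycles, so the information cannot be recovered. At stake is the description of elimination after a 5-day infusion. No escalation or DLT rule uses it.

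**Working it through.** The plan gives no precision figure for this aim, so there is none to reproduce.

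**Inputs**
- Half-life 2.5 h (Section 1.2.1.4, from 30-minute infusions; an assumption for continuous infusion). k = ln 2 / 2.5 = 0.277 per hour.
- Sampling times from Section 5.1.1.
- Residual CV of a concentration: not in the documents; assumed 10%, 20% and 30%. On the log scale σ = √ln(1 + CV²) = 0.100, 0.198 and 0.294.

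**Step 1: how far the decline is followed.** Fraction left = exp(−kt).
- 4 h: 4 / 2.5 = 1.6 half-lives, 33% left. With a half-life of 2, 3 or 5 h, this becomes 25%, 40% or 57%.
- 8 h: 3.2 half-lives, 11% left.
- 24 h: 9.6 half-lives, 0.13% left.

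**Step 2: precision of one patient's slope.** For a log-linear fit, relative SE = σ / (k √Sxx), where Sxx = Σ(t − mean t)².

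| Post-infusion times (h) | Sxx | CV 10% | CV 20% | CV 30% |
|---|---|---|---|---|
| 0.17, 0.5, 1, 2, 4 (as written) | 9.52 | 12% | 23% | 34% |
| 0 added | 11.48 | 11% | 21% | 31% |
| 30-minute draw moved to 8 h | 39.02 | 6% | 11% | 17% |
| the same, with 0 added | 46.69 | 5% | 10% | 16% |

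Worked case, as written at CV 20%: 0.198 / (0.277 × √9.52) = 0.23. The 8 h point brings nearly all the gain. The end-of-infusion sample adds little to the slope but fixes the starting level.

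**Step 3: on the half-life scale.** The 90% range is 2.5 / (1 ± 1.645 × relative SE). At CV 20% this is 2.5 / 1.38 to 2.5 / 0.62 = 1.8 to 4.0 h as written. With the moved draw and an end-of-infusion sample it is 2.5 / 1.17 to 2.5 / 0.83 = 2.1 to 3.0 h.

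**Step 4: would 8 h be measurable?** From the bolus trial, volume = dose / Cmax, clearance = k × volume, and plateau = infusion rate / clearance. Across the three Cmax values this gives plateaus from 1,894 pg/mL (3 mcg/kg/day) to 11,972 pg/mL (5 mcg/kg/day). At 8 h, 0.109 × these = about 206 to 1,303 pg/mL; at 24 h, about 2.4 to 15.4 pg/mL. The documents give no quantification limit, but 8 h is far less exposed to one than 24 h.

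**Step 5: using the onset samples as well.** The same patients are sampled at 10 min, 1, 2, 4, 8, 12, 24 and 48 h and on days 4 and 5 of the infusion. In a one-compartment model the rise follows the same k. A joint fit of one plateau and one k to onset and decline gives a 90% range of about 2.1 to 2.9 h at CV 20%, similar to the changed design.

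That fit forces one k on both phases. In a noise-free check with half-life 2.5 h at onset and 1.5 h at the end, it returned 1.85 h when the plateau was held unchanged. It returned about 1.4 h when the plateau fell in step with rising clearance at constant volume. The error can therefore go either way and can be small.

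**The case against.** The strongest objection is Step 5: half-life does not rest on the post-infusion series alone, and data already planned bring one patient's estimate to about the precision of the changed design. This stands, provided clearance is constant. The protocol gives reason for doubt. Section 1.2.1.3 reports generally lower day-10 levels in macaques during course 1 and suggests the expanded pool of IL-15-responsive cells as a possible cause. Section 8 plans to study concentration changes accompanying the expected lymphocytosis. Only samples after stopping measure the decline without that assumption.

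Four stronger readings are tempting, and the documents do not support them.

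- **The ±30-minute window causes the imprecision.** Neither schedule gives the 10- and 30-minute draws a window of their own, and the stated one can be read as covering only 1, 2 and 4 h. Even if it covered all draws, times are recorded on every tube. At CV 20% the relative SE is 23.1% with exact times and 23.3% with recorded times.
- **The gap falls exactly where dosing is highest.** Only 5 mcg/kg/day exceeds the 10-day range, which reached 4. Per cycle the 5-day levels give 15 to 25 mcg/kg, against 40 at the top 10-day level.
- **The noise cannot be averaged away.** At CV 20% the sampling error of a mean is 23.1% / √9, about 8%, with nine patients, and 23.1% / √21, about 5%, with 21, ignoring variation between patients.
- **The 10-day schedule truly follows the decline to 24 h.** With 0.13% of plateau left, that sample may not be quantifiable.

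It is also fair that the 5-day bullet is headed as being at completion of infusion, so an end-of-infusion sample may be intended.

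**Conclusion.** The point holds as a minor one. The 5-day list ends at 4 h, about 1.6 half-lives, and does not clearly include the end-of-infusion sample that the 10-day list states. From post-infusion samples alone, one patient's slope has a relative SE of about 12% to 34% over the assumed CVs. Moving one draw to 8 h halves that at every CV, so the comparison does not depend on the CV chosen; only the absolute widths do.

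The result rests on mono-exponential decline, on a half-life carried over from 30-minute infusions, and on an 8 h level above the assay limit. The aim is exploratory and the onset samples offer a partial, model-dependent substitute. A reader should not infer that the 5-day PK is uninformative, or that any dose decision is affected.

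**What to change.** In the 5-day list of Section 5.1.1:

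1. State an end-of-infusion sample, drawn before the pump is stopped, as in the 10-day list.
2. Move the 30-minute sample to 8 h, or add an 8 h sample. Otherwise, state that only the first 4 h of decline will be described.
3. State that PK calculations use the recorded draw times. While editing, say which window applies to the 10- and 30-minute draws on both schedules.

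Moving the draw keeps five timed samples after stopping. The cost is protocol wording, one 4 mL tube for the end-of-infusion sample, about 4 more hours on day 6 and, if the draw is moved rather than added, the loss of one early point. That loss would matter mainly for an early distribution phase.
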